4.4 Sample Size and Power

The sample size was calculated based on the mean difference in the cross-sectional area of the FSO by CT at Day 30 between the treatment and control sides from subjects in the PROGRESS study who underwent bilateral frontal BSD followed by unilateral placement of PROPEL Contour with the following assumptions:

- Expected mean difference of 9 mm² between the treatment and control sides
- A standard deviation (SD) of 18 mm² for side-to-side difference
- Target power of 95%
- Type I error rate of $\alpha = 0.05$, 2-sided

Internal, unpublished data suggest that SD = 18 is a reasonable assumption and that an achievable difference in mean cross-sectional areas of the FSO may be greater than 9 mm². The 9 mm² is deemed to be a clinically important difference to detect. Based on standard formulas for a t-test, a sample size of 56 subjects provides at least 95% power to detect a difference of 9 mm² in mean FSO cross-sectional area between treatment side and control side. Assuming up to 20% of subjects

with non-evaluable data on one or both sides, as it was reported in PROGRESS study report (R 28020), an additional 24 subjects will be enrolled for a total of 80 randomized subjects. Sample size calculations were carried out in PASS 14 (PASS 2015).

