6.2 Baseline

The baseline is defined as the last observation recorded prior to the initiation of the study treatment (i.e., PROPEL Contour placement on the treatment site following successful BSD procedure) and referred to as Day 0.

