9.3.4 Sensitivity Analyses

Sensitivity analysis for medical or surgical intervention

Because intervention with oral steroids or surgical intervention may confound the primary efficacy endpoint, the following method will be applied to the analyses in cases where such interventions are performed:

- If a subject initiates oral steroids or undergoes revision ESS for CRS conditions attributable to the FSO/frontal recess before Day 45, this represents treatment failure. If the intervention occurs on the treatment side or both sides, the FSO cross-sectional area of the treatment side will be imputed with the value of the control side (i.e., side-to-side difference in FSO area is

zero). If the intervention occurs on the control side only, the FSO cross-sectional area in the control side will be imputed as zero (i.e., totally occluded).

- If a patient initiates oral steroids for other reasons not involving the FSO/frontal recess before Day 45, this does not represent treatment failure. In this scenario, the side-to-side difference in FSO cross-sectional area for that subject will be imputed as zero.
- No other data imputation rules will be applied in the planned statistical analyses.

Sensitivity analysis for missing data

Subjects with a missed visit, lost to follow-up, or with FSO cross-sectional area ‘unable to view’ by the independent, blinded reviewer will be considered as missing data. If more than 10% of the primary efficacy data are missing, the following imputation analyses will be performed to test the robustness of the primary efficacy conclusion in order:

- *Worst-case imputation.* The worst case of side-to-side difference in FSO area is zero. If the primary efficacy endpoint passes (p -value < 0.05) using worst-case imputation, then there is no need to do a best-case imputation analysis.
- *Best-case imputation.* The best case of side-to-side difference in FSO area is equal to the average for the treatment site.

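### SAP 9.3.4: the best-case fill for missing Day 45 data is ambiguous, gives no valid p-value on either reading, and matters only after the worst case fails, with no rule for interpreting it

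*SAP*

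**What the plan says.** The primary quantity is a within-subject difference: Day 45 FSO area on the treatment side minus area on the control side (SAP 9.3.1 and 9.3.2). Success requires a significant t-test favouring the treatment side, and that rule is stated under the primary analysis (SAP 9.3.3).

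SAP 9.3.4 deals with missing primary data. Nothing is triggered unless more than 10% are missing. Two fills are then run in order, to test how robust the primary conclusion is. The worst case sets the missing difference to zero. If that analysis gives p < 0.05, "then there is no need to do a best-case imputation analysis". The best case is one sentence: "The best case of side-to-side difference in FSO area is equal to the average for the treatment site".

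The SAP does not define *treatment site*. SAP 6.2 uses the phrase for the implanted side: "PROPEL Contour placement on the treatment site following successful BSD procedure". The SAP does not say what a best-case result means once the worst case has failed.

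**The concern.** The value to be filled is a difference, but the sentence supplies an average for one side. There are two plausible readings.

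- **Literal reading.** The fill is the mean area on the implanted side with nothing subtracted for the control side. This amounts to assuming that the control ostium of every subject with missing data is fully closed.
- **Charitable reading.** The fill is the mean observed side-to-side difference. That is not a best case. It leaves the estimate where it was and adds subjects with no variability, so the standard error is too small.

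The order adds to the problem. The best case is declared unnecessary when the worst case passes, so in practice it carries weight only after the worst case fails. At that point the plan offers a favourable computation, in a section about robustness, with no statement of how to read it.

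**Working it through.** **Inputs from SAP 4.4.** "Expected mean difference of 9 mm² between the treatment and control sides"; "A standard deviation (SD) of 18 mm² for side-to-side difference"; two-sided 0.05; 80 randomized; up to 20% non-evaluable (16 of 80). The trigger of more than 10% means at least 9 of 80.

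**Assumption.** The treated-side mean area A is not in the documents. I used 20, 28.3 and 40 mm². The middle value is the circle of the 6 mm balloon, π × 3² = 28.3. It is only a reference point, because the endpoint is mucosal area at the minimum diameter at Day 45.

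**1. The plan's own figure.** The SAP states that "a sample size of 56 subjects provides at least 95% power to detect a difference of 9 mm²". A paired t-test (noncentral t, effect 9/18 = 0.5) needs n = 54 for 95.0% power, and n = 56 gives 95.7%. The figure is reproduced, which confirms that 18 is the SD of the within-subject difference.

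**2. Literal fill, formula.** Let N = 80, with m missing and k = N − m observed, observed mean d and observed SD s.

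- Filled mean = (k·d + m·A)/N
- Sum of squares SS = (k − 1)s² + (mk/N)(A − d)²
- t = filled mean / √(SS/[(N − 1)N])

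Take an observed difference of exactly zero, s = 18, m = 16 and A = 40. The mean is 16 × 40/80 = 8.0. SS = 63 × 324 + (16 × 64/80) × 1600 = 20,412 + 20,480 = 40,892. The SE is √(40,892/(79 × 80)) = 2.54, so t = 3.15 and p = 0.002. The fill alone produces this result. With d = 0 and s = 18, p falls below 0.05 once A reaches about 20 mm² (16 missing) or 43 mm² (9 missing).

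If the true difference is 9 and A = 28.3 with 16 missing, the expected estimate becomes 0.8 × 9 + 0.2 × 28.3 = 12.9.

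**3. Literal fill, simulation.** True difference 0, SD 18, at least 100,000 trials per setting, counting p < 0.05 in favour of the implant (nominal 2.5%):

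| Missing of 80 | A = 20 | A = 28.3 | A = 40 |
|---|---|---|---|
| 9 | 19% | 29% | 46% |
| 16 | 50% | 75% | 93% |

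Among trials whose worst case failed, the rates are about 16%, 27% and 45% with 9 missing, and 49%, 74% and 93% with 16 missing. Even A = 9 mm² gives 7.5% and 15.9% over all trials.

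**4. Mean-difference reading.** The estimate does not change. The SE is multiplied by √[k(k − 1)/(N(N − 1))].

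- 9 missing: √(71 × 70/6320) = 0.887. The effective cut-off is 1.990 × 0.887 = 1.765 on 70 df, so the two-sided false-positive rate is 8.2%.
- 16 missing: √(64 × 63/6320) = 0.799. The cut-off is 1.590 on 63 df, so the rate is 11.7%.

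**5. What the worst case does.** Filling with zero shrinks the mean and the SE by nearly the same factor. With 64 observed and t = 2.00 (p = 0.0498), the zero fill gives t = 1.99 (p = 0.0500). In simulations with 9 or 16 missing and a true difference of 0, 3, 5 or 9, the primary test passed while the zero fill failed in at most about 0.06% of trials. With no true effect, over 99.9% of best-case passes that followed a worst-case failure came from trials whose primary analysis had also failed.

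**The case against.** The strongest reply is that this is a sensitivity analysis and cannot change the trial's conclusion. That stands. A reader might infer from the rates above that the best case could turn a failed trial into a success. The documents do not support this: 9.3.3 puts the success rule on the primary analysis, and step 5 shows that the affected trials have nearly all failed it already.

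A reader might also infer that p < 0.05 is the pass mark for the best case. In the text that mark belongs to the worst-case step only, and no criterion is attached to the best case. Nor is the best case forbidden when the worst case passes; the wording is permissive.

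It can also be said that a best case is favourable by design, so its false-positive rate is the wrong yardstick, and that 9.3.4 itself sets a control side to zero area after an intervention on that side only. This is fair for a bound shown as one end of a range. The plan, however, extends the closed-ostium assumption to missed visits, loss to follow-up and unreadable scans, and does not label the result as a bound.

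Finally, it is too strong to say that the step can only help the implant. With 9 missing and no effect, the literal best case still fails in about 55% to 84% of worst-case failures (A from 40 down to 20), which would count against the implant. Under the mean-difference reading the inflation runs in both directions.

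**Conclusion.** The point holds as a defect in a sensitivity analysis and should be corrected before the primary analysis. The best-case sentence has two readings and neither gives a valid p-value. The literal reading is favoured by SAP 6.2, but that is a single loosely worded use, so the intended meaning is not certain.

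The size depends on the reading, on the number missing and, for the literal reading, on an assumed treated-side area. Sixteen missing is the top of the SAP's own allowance, and nine is the smallest number that triggers the step with 80 subjects. The favourable false-positive rate exceeded 2.5% at every area tried.

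The consequence is limited to reporting: a favourable-looking robustness result could appear beside a failed primary analysis with no rule for discounting it. The companion worst case does little to balance it, because zero is the null value and not an outcome unfavourable to the implant.

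**What to change.** In SAP 9.3.4:

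1. Delete the sentence that makes the best case unnecessary when the worst case passes.
2. Replace the best-case bullet with a favourable bound defined explicitly on the treatment-minus-control scale.
3. Pair it with an unfavourable bound in which the missing difference is below zero, and always report the two together. A tipping-point analysis over a range of assumed differences would do both.
4. State that neither bound carries a p < 0.05 pass reading, and that neither can support effectiveness if the primary analysis fails.

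Deleting the best case alone is not enough, because it would leave only the zero fill, which nearly repeats the primary p-value.

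The cost is a few sentences of SAP text, a little more analysis, and the loss of one favourable-looking sensitivity result. No new data, visits or subjects are needed.

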9.3.5 Subgroup Analyses

The primary efficacy endpoint will be examined using the following subgroups that are of interest in assessing the treatment effect of PROPEL Contour. The analysis of the primary endpoint may be performed if each subgroup represents at least 10% of the ITT population.

- Age (< 65 vs. ≥ 65)
- Gender (male vs. female)
- Previous frontal BSD (Yes vs. No)
- Ethmoid polyp grade (Yes vs. No)

9.4 Key Secondary Endpoints

- Cross-sectional area of the FSO change from baseline to Day 45 on CT by an independent, blinded reviewer
- FSOT volume at Day 45 on CT by an independent, blinded reviewer
- FSO minimum diameter at Day 45 on CT by an independent, blinded reviewer
- Zinreich’s modified Lund-Mackay score for the frontal sinus at Day 45 on CT by an independent, blinded reviewer

- Need for post-operative intervention in the frontal recess/FSO by clinical investigators at Day 45

See Section 9.2.1 for the definitions for these endpoints.

9.4.1 Multiplicity Adjustment for Key Secondary Endpoints

Intersect ENT intends to present inferential statistical results to support product labeling claims for 5 key secondary endpoints. This section describes the methods that will be used to control the familywise type 1 error rate (FWER) among the tests of these 5 secondary endpoints. All other secondary endpoints will be viewed as exploratory or explanatory in nature.

1. Cross-sectional area of the FSO change from baseline to Day 45 on CT by an independent, blinded reviewer
Test: $H_0: \mu = 0$ vs $\mu \neq 0$ by t-test
2. FSOT at Day 45 on CT by an independent, blinded reviewer
Test: $H_0: \mu = 0$ vs $\mu \neq 0$ by t-test
3. FSO minimum diameter at Day 45 on CT by an independent, blinded reviewer
Test: $H_0: \mu = 0$ vs $\mu \neq 0$ by t-test
4. Zinreich's modified Lund-Mackay score for frontal sinus at Day 45 on CT by an independent, blinded reviewer
Test: $H_0: \mu = 0$ vs $\mu \neq 0$ by t-test
5. Need for post-operative intervention by clinical investigators at Day 45

Test: $H_0: p_T = p_C$, where p_T and p_C are the probability of needing post-operative intervention on the treatment and control sides, respectively. Tested by McNemar's test (exact version).

Let $p_{(1)} \leq p_{(2)} \leq \dots \leq p_{(m)}$ be the $m=5$ p-values resulting from the above 5 tests, after being placed in ascending order. Adjusted p-values $\tilde{p}_{(1)}, \dots, \tilde{p}_{(m)}$ from Holm's step-down procedure will be calculated as follows:

$$\tilde{p}_{(i)} = \begin{cases} mp_{(1)} & \text{for } i = 1 \\ \max\left(\tilde{p}_{(i-1)}, (m-i+1)p_{(i)}\right) & \text{for } i = 2, \dots, m \end{cases}$$

Source: SAS Institute Inc. 2008. *SAS/STAT® 9.22 User's Guide*. Cary, NC: SAS Institute Inc., p 4839.

If any adjusted p-value exceeds 1, it is set to 1. Using this procedure, any adjusted p-value that is < 0.05 is statistically significant and supports a claim for the corresponding endpoint, while any

CONFIDENTIAL

25 of 33

May not be reproduced outside of Intersect ENT without written permission from Document Control

adjusted p-value ≥ 0.05 is not statistically significant. Both adjusted and unadjusted p-values will be reported.

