### **18.3 Analysis of Key Secondary Efficacy Endpoints**

To support potential device labeling claims, a subset of secondary endpoints at Day 45 will be identified and analyzed using appropriate methods for controlling for family-wise type error rate (FWER). This will be detailed in the SAP that will be prepared prior to the primary analysis.

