6.7 Missing Data for Efficacy and Safety Endpoints

Missing data for each efficacy endpoint will be handled as described in Sections 9.1 and 9.3.4.

For continuous endpoints, change from baseline will be set to missing at visits with missing postbaseline values or where data were imputed to missing. Continuous efficacy endpoints will be set to missing for subjects who received any of the following not allowed medication post-baseline procedure:

- Corticosteroids (e.g., oral, parenteral or injection, budesonide or other sinus steroid irrigations/rinses or drops, breath powered Xhance, nebulized steroids administered nasally or other drug eluting stents) through Day 45; or
- Biologics for CRS treatment (e.g., Dupixent).

For binary endpoints, subjects with missing efficacy data, early withdrawals, and/or subjects who received not allowed corticosteroids or biologics for chronic sinusitis condition attributable to the FSO/frontal recess will be imputed as a treatment failure. If a subject initiates high-dose steroid for other reasons not involving FSO/frontal recess, this does not represent treatment failure.

Additional rules for handling of missing data and rescue treatments are detailed below:

- *Missing efficacy data.* Visits with missing data (due to a missed visit or missing component of a composite endpoint) will be set to treatment failure.
- *Early withdrawals.* Only visits following the early withdrawal visit will be set to treatment failure.
- *Rescue treatments.* Subjects who rescue with corticosteroids (before Day 45) or biologics will be set to treatment failure at all subsequent visits and continuous endpoints set to missing.
- *Missing baseline value.* For efficacy endpoints, a missing value at baseline will not be imputed, and the endpoint will be set to missing for all visits.

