9.2 Clinical Variables

9.2.1 CT Endpoints

The independent, blinded reviewer will perform computer assisted measurements in the FSO and frontal sinus outflow tract (FSOT) according to a validated protocol (See CP-00038).

Cross-sectional area of the FSO

The cross-sectional area within the mucosa and the bone at the location of the measured minimum diameter between 5 mm superior and 5 mm inferior to the ostium. It will be reported in mm² for the mucosa and bone for the left and right ostia separately. This measurement will be repeated at the location 5 mm superior and 5 mm inferior to the ostium.

FSO minimum diameter

The minimum diameter as output by the segmentation software at the FSO reference plane between the boundaries of the mucosa and bone, representing the pneumatized portion of the ostium (with mucosa as boundaries) or the pneumatized and mucosal portions of the ostium (with bone as boundaries). It will be reported in mm for the left and right ostia separately. This measurement will be repeated at the CT slice corresponding to the location 5 mm superior and 5 mm inferior to the ostium.

FSOT volume

The volume of the patent frontal sinus outflow tract (FSOT) between boundaries of the mucosa located 5 mm superior and 5 mm inferior to the ostium in the 3D volume segmentation of the FSOT. It will be reported in mm³ and measured separately for the left and right FSOT. This space

corresponds to the implant location. The measurements will be repeated for the volume of mucosal and patent FSOT (i.e., with bone as boundaries).

Zinreich's modified Lund-Mackay score

Each sinus is assigned a score based on the percentage of opacification from mucosal thickening as follows:

- 0: 0%
- 1: 1% to 25%
- 2: 26% to 50%
- 3: 51% to 75%
- 4: 76% to 99%
- 5: 100% or completely occluded

The ostiomeatal complex (OMC) is given a score of 0 if it is completely patent, 1 if it is partially obstructed, or 2 if it is completely obstructed. Similar to the Lund-Mackay system, each side is graded, and their sum is the total score out of maximum of 54.

Lund-Mackay score

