9.3.1 Definition

The cross-sectional area will be determined by the independent, blinded reviewer on CT at Day 45 within the mucosa at the location of the measured minimum diameter between 5 mm superior and 5 mm inferior to the ostium. It will be reported in mm² for the left and right ostia separately.

For each subject, the difference between FSO cross-sectional area at Day 45 in the treatment and control sides will be calculated and then averaged across all subjects in the ITT population. The FSO cross-sectional area will be set as missing if the FSO is unable to be viewed or measured.

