9.3.3 Primary Analysis

The primary statistical method is a t-test comparing the mean FSO cross-sectional area at Day 45 in the treatment and control sides.

The study will be considered successful if there is a statistically significant difference in mean FSO cross-sectional area in favor of the treatment side. Although the alternative hypothesis is two-sided, only a statistically significant difference in average FSO area favoring the treatment side will constitute evidence of effectiveness.

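### The Holm procedure in SAP 9.4.1 covers only the five key secondary endpoints and is not conditional on primary success, so as written a failed primary can still yield a labeling claim

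*SAP*

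**What the plan says.** Protocol 18.3 gives the purpose of the key secondary endpoints: "To support potential device labeling claims, a subset of secondary endpoints at Day 45 will be identified". It asks for familywise error control and leaves the method to the SAP.

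SAP 9.4.1 names five endpoints, all at Day 45: change from baseline in FSO area, FSOT volume, FSO minimum diameter, Zinreich score for the frontal sinus, and need for post-operative intervention. It undertakes to "control the familywise type 1 error rate (FWER) among the tests of these 5 secondary endpoints", applies Holm's step-down method with m = 5, and gives the decision rule: "any adjusted p-value that is < 0.05 is statistically significant and supports a claim for the corresponding endpoint".

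The primary endpoint is outside that family. SAP 9.3.3 tests it with a two-sided t-test, and 9.3.2 gives the hypotheses; 4.4 and 6.1 set the level at 5%. Section 9.3.3 defines study success by the primary alone and adds that "only a statistically significant difference in average FSO area favoring the treatment side will constitute evidence of effectiveness". No testing order or gate linking the primary to the key secondaries appears in Protocol 18.3 or in SAP 5.2 (with Table 1), 5.3, 6.1, 9.3.3, 9.4 or 9.4.1.

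**The concern.** The five tests exist to support labeling, so the rule that lets them do so should say what happens when the primary fails. Section 9.4.1 is otherwise fully operational, down to capping adjusted p-values at 1, and its only condition for a claim is the Holm-adjusted p-value. There are therefore two separate families, each with its own 5%, and the chance of a false claim over the primary and key secondaries together exceeds that of the primary alone.

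The least protected case is need for post-operative intervention. Investigators rate it, and Protocol 19.3 says they are unblinded. As written, it could support a claim on its own after the blinded CT primary had failed.

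A smaller gap is direction. Section 9.3.3 states that only a difference favouring treatment counts; 9.4.1 uses two-sided tests and does not repeat that condition.

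**Working it through.** **Inputs.** From SAP 4.4: difference 9 mm², SD of the side-to-side difference 18 mm², two-sided α = 0.05, 56 evaluable subjects, 80 randomized, up to 20% non-evaluable. From SAP 9.4.1: Holm, m = 5. Correlations among the six endpoints are not given and are assumed.

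**The SAP's own sample size.** SAP 4.4 states: "Based on standard formulas for a t-test, a sample size of 56 subjects provides at least 95% power to detect a difference". For a t-test on the within-subject difference, the noncentrality is (9/18)·√n. The noncentral t distribution gives power 0.950 at n = 54 and 0.957 at n = 56, so the statement holds. With 20% of 80 non-evaluable, n = 80 × 0.80 = 64 and power is 0.976.

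**How a claim can follow a failed primary.** Suppose the primary p = 0.20 and the key secondary p-values are 0.004, 0.03, 0.2, 0.4 and 0.6. Holm gives 5 × 0.004 = 0.02; 4 × 0.03 = 0.12; 3 × 0.2 = 0.60; 2 × 0.4 = 0.80; max(0.80, 0.6) = 0.80. The first endpoint supports a claim under 9.4.1, although the study is not successful under 9.3.3.

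**Error rate when there is no effect on any endpoint.** Six normal test statistics with a common correlation ρ were simulated (8,000,000 draws per ρ), with full Holm step-down on the five secondaries, counting only results that favour treatment. The exact McNemar test for endpoint 5 is approximated by a normal statistic.

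| Assumed ρ | Any favourable false claim, as written | With a favourable-primary gate | Secondary claim without primary success, as written |
|---|---|---|---|
| 0 | 4.9% | 2.5% | 2.4% |
| 0.3 | 4.6% | 2.5% | 2.1% |
| 0.5 | 4.1% | 2.5% | 1.6% |
| 0.7 | 3.5% | 2.5% | 1.0% |
| 0.9 | 2.7% | 2.5% | 0.2% |

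The gated figure is half of the two-sided 5%. Check at ρ = 0: 1 − 0.975² = 4.94%, against 4.93% simulated.

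**What the documents say about correlation.** Endpoint 1 subtracts a baseline value. With equal SDs at baseline and Day 45 (assumed) and a baseline–Day 45 correlation r, its correlation with the primary is √((1 − r)/2): 0.71, 0.50 and 0.39 at r = 0, 0.5 and 0.7. Minimum diameter is defined as "The minimum diameter as output by the segmentation software at the FSO reference plane", whereas the primary area is taken "within the mucosa at the location of the measured minimum diameter between 5 mm superior and 5 mm inferior to the ostium"; the two need not be read in the same plane. Endpoint 5 is not a CT measure at all. A uniformly high correlation therefore cannot be taken for granted.

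**What a gate would cost.** The upper bound is the chance that the primary fails, 1 − power (noncentral t, SD 18 mm²). Only 9 mm² is the SAP's value; the smaller effects are assumed.

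| True difference | n = 56 | n = 64 |
|---|---|---|
| 9 mm² | 4.3% | 2.4% |
| 8 mm² | about 10% | about 6% |
| 7 mm² | 18.4% | 13.5% |
| 6 mm² | 31.2% | 25.3% |

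The share of trials in which a favourable secondary claim would actually be blocked is smaller. If all six endpoints share the primary's standardized effect (assumed; normal approximation, mean (d/18)·√n with d the true difference, 1,000,000 draws):

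| True difference | n | ρ = 0 | ρ = 0.5 | ρ = 0.9 |
|---|---|---|---|---|
| 9 mm² | 56 | 3.7% | 3.4% | 0.7% |
| 9 mm² | 64 | 2.1% | 1.9% | 0.4% |
| 7 mm² | 56 | 17.0% | 12.3% | 1.8% |
| 7 mm² | 64 | 12.5% | 9.7% | 1.6% |
| 6 mm² | 56 | 28.4% | 17.3% | 2.3% |
| 6 mm² | 64 | 23.5% | 15.4% | 2.2% |

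**The case against.** The scope is stated openly: 9.4.1 promises error control among the five secondaries and delivers it, and Protocol 18.3 asks for no more. No commitment is broken, and a sponsor may choose two separate 5% families. That stands, but the choice should then be explicit and justified, and neither document says it was made.

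The sentence in 9.3.3 about evidence of effectiveness can be read as settling only which direction of the primary test counts. On that reading 9.4.1 does not conflict with it. This is fair and removes the tension between the sections; the absence of a gate remains.

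A result that supports a claim is not yet a claim in the label. True, but the SAP is where the statistical condition is fixed, and it leaves the case of a failed primary open until after unblinding.

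The harm is modest. The total stays below 5%, and the top of the range needs zero correlation, which is implausible for measures taken from the same scan. At 0.5 to 0.9 the excess is 0.2 to 1.6 points. This stands as to size.

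The gate may also block true claims about as often as it prevents false ones: 0.4 to 2.1% at 9 mm² and n = 64, and more if the effect is smaller. This stands too, and is the real trade-off.

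**Conclusion.** The concern holds. As written, a Holm-adjusted p-value below 0.05 is sufficient for a key secondary endpoint to support a labeling claim, whatever the primary shows. That much is certain from the text. The size is not: the excess chance of a favourable false claim is 0.2 to 2.4 percentage points over the 2.5% of a gated plan, for assumed common correlations from 0.9 down to 0, with no effect on any endpoint and endpoint 5 treated as normal. Holm is valid within its stated scope, and neither the primary test nor the study success rule is affected. This should be corrected, but it does not threaten the primary conclusion.

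**What to change.** Add to SAP 9.4.1: *The five key secondary endpoints are tested for claims only if the primary endpoint is significant (p < 0.05) in favour of the treatment side; otherwise their p-values are descriptive. A claim also requires the difference to favour the treatment side (larger area, volume or diameter; lower Zinreich score; fewer interventions).* Keep Holm inside the gate, and make the change before the Day 45 unblinding described in SAP 5.2.

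The edit changes neither the sample size, the primary test nor the Holm step. Its price is that no key secondary endpoint, including need for post-operative intervention, can support a claim if the primary fails; the tables above give the cost. SAP 6.7 could raise it: "Continuous efficacy endpoints will be set to missing for subjects who received any of the following not allowed medication". If those exclusions come on top of the 20% allowance in 4.4, the evaluable n falls below 64; the SAP does not say whether they are inside it.

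If the sponsor prefers claims that survive a failed primary, 9.4.1 should say so, justify it, and state the resulting error rate over all six tests.

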## 9.2 Secondary Endpoints

- CT grading by an independent, blinded reviewer (Day 45, 180):
  - Cross-sectional area of FSO (Day 180 only)
  - FSO minimum diameter
  - FSOT volume
  - Zinreich's modified Lund-Mackay score for the frontal sinus
  - Lund-Mackay score for the frontal sinus
- CT grading by clinical investigators (Day 45, 180):
  - Lund-Mackay score for the frontal sinus
- Need for post-operative intervention as determined by clinical investigators based on endoscopic evaluation (Day 21, 45, 90, 180):
  - Repeat frontal SBD warranted or performed for restenosis/occlusion in the frontal recess/FSO; or
  - Surgical intervention warranted or performed to debride obstructive adhesions/scarring or for restenosis/occlusion in the frontal recess/FSO; or
  - Oral steroids warranted or prescribed to resolve recurrent edema in the frontal recess/FSO
- Endoscopic grading by clinical investigators (Day 21, 45, 90, 180):
  - Adhesion/scarring grade in the frontal recess/FSO and ethmoid sinus
  - Inflammation score in the frontal recess/FSO
  - Polypoid edema in the frontal recess/FSO
  - Polyp grade in the ethmoid sinus
- Patient-reported outcomes:
  - CRS side-specific symptom score (Day 21, 45, 90, 180)
  - SNOT-22 score (Day 180)
  - RSI score (Day 180)
- Implant delivery success rate by clinical investigators

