9.3.2 Statistical Hypothesis

The primary efficacy hypothesis is that the placement of the PROPEL Contour will significantly increase the FSO cross-sectional area on the treatment side versus the control side. The relevant null and alternative hypotheses for this primary efficacy endpoint are:

$$H_0: \mu = 0$$

$$H_1: \mu \neq 0$$

Where μ represents the mean difference between the treatment and control sides in cross-sectional area of the FSO at Day 45.

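### SAP key secondary 1, change in FSO area to Day 45, is outside the protocol's list of secondary endpoints and gives Day 45 area a second, ungated route to a labeling claim

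*SAP*

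**What the plan says.** Protocol 18.3 says that, for potential labeling claims, "a subset of secondary endpoints at Day 45 will be identified and analyzed using appropriate methods", with the detail left to the SAP. Protocol 9.2, like the Protocol Summary, enters FSO area among the blinded-reader CT secondaries as "Cross-sectional area of FSO (Day 180 only"). Day 45 area is the primary endpoint (Protocol 9.1).

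SAP Table 1, 9.4 and 9.4.1 place "Cross-sectional area of the FSO change from baseline to Day 45 on CT by an independent, blinded reviewer" at the head of a five-endpoint family. It is tested by a t-test of mu = 0 within a Holm procedure with m = 5. For the primary, SAP 9.3.2 says that mu "represents the mean difference between the treatment and control sides in cross-sectional area of the FSO at Day 45". SAP 9.4.1 gives no definition of mu for item 1. SAP 9.4 refers to 9.2.1 for definitions, and 9.2.1 defines the area but no change score.

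SAP 9.4.1 controls the familywise error among the five tests only. It treats any adjusted p-value below 0.05 as supporting a claim, and does not say that the family is tested only after a successful primary.

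**The concern.** Three things are wrong together. The endpoint is not in the set from which the protocol says the key secondaries are drawn. Its estimand is undefined, and neither natural reading yields a claim separate from the primary. With no gate, a trial that misses on Day 45 area could still report a significant area result under a heading that the SAP says supports a claim. At stake is the credibility of a labeling statement about area. A smaller matter is power: while item 1 is not rejected, it raises the Holm multiplier for the other four endpoints.

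**Working it through.** **1. The plan's own figure.** Inputs from SAP 4.4: "Expected mean difference of 9 mm² between the treatment and control sides"; "A standard deviation (SD) of 18 mm² for side-to-side difference"; "Type I error rate of $\alpha = 0.05$, 2-sided"; power 95%. The standardised effect is 9/18 = 0.5. A paired t-test with the noncentral t reaches 95.0% power at n = 54 and 95.7% at n = 56, so the stated 56 is confirmed. With 80 randomised and 20% non-evaluable, 80 × 0.8 = 64 remain.

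**2. Version check.** The SAP says it is based on protocol version 5.0, and both documents carry 20 May 2022. Version lag does not explain the mismatch.

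**3. Reading A: side difference in change.** Write T and C for the area on the treatment and control sides, D0 = T0 − C0 and D45 = T45 − C45.
- (T45 − T0) − (C45 − C0) = D45 − D0.
- The only scheduled pre-treatment CT is the Screening CT (SAP 6.4, Appendix A). Side is randomised afterwards, following the dilation (Protocol 12.3.3, SAP 6.3), so E(D0) = 0.
- Hence E(D45 − D0) = E(D45), which is the primary's mu. The null is the same.

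**4. Reading B: change within a side.** The bilateral dilation takes place between the Screening CT and Day 45. The change on one side therefore contains the dilation effect and is not an implant comparison.

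**5. How different the two statistics are under reading A.** The documents give neither the SD of D0 (s0) nor its correlation r with D45, so both are assumed. With the SD of D45 equal to 18:
- SD of change = √(18² + s0² − 2·r·18·s0)
- correlation with the primary = (18 − r·s0) / SD of change. This becomes √((1 − r)/2) when s0 = 18.

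The null chance that either test is significant is 1 − P(|Z1| < 1.960 and |Z2| < z), with z = 2.576 for the change test at 0.01 and 1.960 at 0.05:

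| s0 | r | SD of change | correlation | change test at 0.01 | change test at 0.05 |
|---|---|---|---|---|---|
| 18 | 0 | 25.5 | 0.71 | 5.5% | 8.3% |
| 18 | 0.5 | 18.0 | 0.50 | 5.7% | 9.1% |
| 18 | 0.8 | 11.4 | 0.32 | 5.9% | 9.5% |
| 9 | 0.5 | 15.6 | 0.87 | 5.2% | 7.3% |

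Simulated t-tests at n = 64 agree within simulation error: about 5.3-6.0% (s0 = 18) and 5.0-5.3% (s0 = 9) at 0.01. The 0.01 column is Holm's first step (0.05/5). The 0.05 column applies only if the other four tests have already been rejected, so it is an upper bound. At 0.01 and s0 = 18, the excess in the implant's favour is about half of the two-sided excess: (5.5 − 5)/2 to (5.9 − 5)/2, or 0.2-0.4% of trials.

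**6. Second chance when there is a real but smaller effect.** Assume a true difference of 4.5 mm², n = 64 and s0 = 18. The primary then misses in about half of trials. Among those misses, the change test favours the implant at 0.01 in about 6%, 14% and 36% (r = 0.3, 0.5, 0.7). At 0.05 the figures are about 19%, 34% and 62%.

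**7. Holm cost.** The steps are 0.0100, 0.0125, 0.0167, 0.025, 0.05 with m = 5 and 0.0125, 0.0167, 0.025, 0.05 with m = 4. In simulation at n = 56, with an assumed standardised effect of 0.35 for each of the other four:
- r = 0 and an area effect also of 0.35: mean power rises from 60.1% to 64.9% when item 1 is removed.
- Planned area effect of 0.5: the gain is 0.5-0.6 points at r = 0.5 and 0.0 points at r = 0.8.

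**8. Overall claim error.** Under the global null at n = 56, the chance of any significant result in the primary or the ungated family is 8.2-9.6% with m = 5 and 8.5-9.7% with m = 4.

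**The case against.** The strongest reply has four parts.

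- **Deferral to the SAP.** Protocol 18.3 and 18.4 leave detail to the SAP, Protocol 9.2 gives no change-from-baseline form for any CT endpoint, and SAP 9.5 adds such forms throughout. The Day 180 restriction may only avoid repeating the primary. This softens the mismatch but does not remove it: the protocol defers which subset and which methods, not additions from outside the list. Adding a line to Protocol 9.2 would align the documents but leave the duplicate test.
- **Study success is protected.** A reader might infer that a change-score result could rescue a failed trial. SAP 9.3.3 rules that out: success rests on the Day 45 side comparison, in the implant's favour. What stays open is a labeling claim under 9.4.1.
- **The gate is the main problem.** This stands. Step 8 shows that removing item 1 leaves the overall claim error essentially unchanged, and a gate alone would close the second route. A reader might expect deletion to restore 5%; it does not.
- **Large figures mislead.** This also stands. The 8-9.5% needs four prior rejections, including minimum diameter and FSOT volume from the same region, which is unlikely with no area effect. The 19%, 34% and 62% assume a true benefit, so they are not false-claim rates. Equal baseline and Day 45 SDs are an assumption; the baseline scan precedes dilation.

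A reader might also infer that item 1 takes a Holm share that the other four cannot do without. Holm passes that share on in full once item 1 is rejected.

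**Conclusion.** The point holds in moderate form. That the endpoint is outside the protocol's list and that its mu is undefined follow from the documents without any numerical assumption. So does the conclusion that neither reading supports a separate implant claim: one repeats the primary's null, and the other is not a treatment comparison.

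The numerical harm is limited: less than about one percentage point of either-test error at Holm's first step, close to nominal if the baseline side difference varies less than the Day 45 one, and 0-5 points of power for the other endpoints. These sizes rest on assumed values of s0 and r, on 64 evaluable subjects for the error rates, and on assumed effects for the other four endpoints at n = 56 for the Holm cost. It is worth correcting because the edit is small and the claim at issue is the primary's own.

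**What to change.** 1. In SAP 9.4, 9.4.1 and Table 1, remove item 1 from the key secondary family and set m = 4 in the Holm formula.
2. Report the side difference in change in FSO area as a supportive analysis of the primary. Define mu explicitly as the mean of (T45 − T0) − (C45 − C0), and attach no separate claim.
3. State in SAP 9.4.1 that the Holm family is tested for claims only if the primary succeeds. Step 1 alone does not control the overall claim error.

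The cost is SAP wording, one constant in the Holm program and one gating condition. The sponsor gives up a separate change-in-area claim and, through the gate, any key secondary claim after a missed primary.
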